4.5.15.3 EuroQol 5-Dimension Questionnaire

The EQ-5D is a generic preference-based health-related quality of life questionnaire that provides a single index value for health status (Rabin and de Charro 2001). This tool includes questions about mobility, self-care, usual activities, pain/discomfort, and anxiety/depression that are used to build a composite of the patient's health status. The EQ-5D questionnaire will be utilized in this study for economic modeling. A copy of the questionnaire is provided in [Appendix 7](#).

4.5.15.4 Borg Category Ratio 10 Scale®

The Borg CR10 Scale is a one-item assessment that can be used to measure a variety of perceptions and experiences (i.e., perceived exertion, chest pain, dyspnea, and fatigue) (Borg and Borg 2010). In this study, the instrument will be used to assess dyspnea from the patient's perspective. The Borg CR10 Scale ranges from 0 (Nothing at all) to 10 • (Absolute maximum/Highest possible). A copy of the assessment is provided in [Appendix 12](#).

4.5.16 Optional Samples for Roche Clinical Repository

4.5.16.1 Overview of the Roche Clinical Repository

[REDACTED]

[REDACTED]

[REDACTED]

[REDACTED]

[REDACTED]

- [REDACTED]

4.5.16.2 Approval by the Institutional Review Board or Ethics Committee

Sampling for the RCR is contingent upon the review and approval of the exploratory research and the RCR portion of the Informed Consent Form (ICF) by each site's Institutional Review Board (IRB) or independent Ethics Committee (IEC) and, if applicable, an appropriate regulatory body. If a site has not been granted approval for RCR sampling, this section of the protocol will not be applicable at that site.

4.5.16.3 Sample Collection

The following samples will be collected for identification of dynamic (non-inherited) biomarkers:

- Residual PD and PK serum samples for research purposes, including but not limited to research on biomarkers related to IL-13, IPF, IPF-related diseases, or other respiratory diseases
- Whole-blood PAXgene samples for RNA extraction for research purposes including but not limited to research on biomarkers related to IL-13, IPF, IPF-related diseases, or other respiratory diseases

The following samples will be collected for identification of genetic (inherited) biomarkers:

- Whole-blood samples for DNA extraction for research purposes, including but not limited to research on biomarkers related to IL-13, IPF, IPF-related diseases, or other respiratory diseases

The purpose of collecting optional RNA samples is to increase the understanding of peripheral blood gene expression in patients with IPF with and without lebrikizumab. These studies may help identify biomarkers to increase understanding of disease severity, disease progression, and clinical heterogeneity of the disease and possible drug response.

The purpose of collecting the optional DNA sample is to study genetic determinants that may predict response to lebrikizumab and other therapies used or that will be used for treatment of IPF, as well as to understand the relationship between heritable factors and clinical features of IPF. These studies might also help to increase understanding of the disease.

For all samples, dates of consent and specimen collection should be recorded on the associated RCR page of the eCRF. For sampling procedures, storage conditions, and shipment instructions, see the Sample Handling and Logistics Manual.

RCR specimens will be destroyed no later than 15 years after the date of final closure of the associated clinical database. The RCR storage period will be in accordance with the IRB/IEC-approved ICF and applicable laws (e.g., health authority requirements).

The dynamic biomarker specimens will be subject to the confidentiality standards described in Section 8.4. The genetic biomarker specimens will undergo additional processes to ensure confidentiality, as described below.

4.5.16.4 Confidentiality

[REDACTED]

[REDACTED]

[REDACTED]

[REDACTED]

[REDACTED]

4.5.16.5 Consent to Participate in the Roche Clinical Repository

The ICF will contain a separate section that addresses participation in the RCR. The investigator or authorized designee will explain to each patient the objectives, methods, and potential hazards of participation in the RCR. Patients will be told that they are free to refuse to participate and may withdraw their specimens at any time and for any reason during the storage period. A separate, specific signature will be required to document a patient's agreement to provide optional RCR specimens. Patients who decline to participate will not provide a separate signature.

The investigator should document whether the patient has given consent to participate by completing the RCR Research Sample Informed Consent eCRF.

In the event of an RCR participant's death or loss of competence, the participant's specimens and data will continue to be used as part of the RCR research.

4.5.16.6 Withdrawal from the Roche Clinical Repository

[REDACTED]

4.5.16.7 Monitoring and Oversight

RCR specimens will be tracked in a manner consistent with Good Clinical Practice by a quality-controlled, auditable, and appropriately validated laboratory information management system, to ensure compliance with data confidentiality as well as adherence to authorized use of specimens as specified in this protocol and in the ICF. Roche monitors and auditors will have direct access to appropriate parts of records relating to patient participation in the RCR for the purposes of verifying the data provided to Roche. The site will permit monitoring, audits, IRB/IEC review, and health authority inspections by providing direct access to source data and documents related to the RCR samples.

4.5.17 Timing of Study Assessments

4.5.17.1 Screening and Pretreatment Assessments

Written informed consent for participation in the study must be obtained before performing any study-specific screening tests or evaluations. ICF completion must occur before any other Visit 1 procedures are initiated.

ICFs for enrolled patients and for patients who are not subsequently enrolled will be maintained at the study site.

Screening tests and evaluations will be performed within 28 ± 14 days prior to randomization (Day 1, Visit 2) or the start of run-in (Visit 1.5), where required, unless otherwise specified. For Cohort B, all screening evaluations must be completed and reviewed to confirm that patients meet all eligibility criteria before the pirfenidone titration run-in period (Visit 1.5) and/or randomization Visit 2 are scheduled. A minimum period of 4 weeks may be required to establish pirfenidone tolerability prior to the randomization

visit (Day 1, Visit 2) for patients in Cohort B. The investigator will maintain a screening log to record details of all patients screened and to confirm eligibility or record reasons for screening failure, as applicable.

A serum sample to assess periostin must be collected and shipped to the central laboratory during the first 2 weeks of screening.

Re-screening refers to repeating the entire screening process, with the exception of HRCT/SLB results. Re-screening is required if a patient has not met all of the eligibility criteria within the screening period. Patients are allowed to be re-screened for selected reasons up to two times. Each patient must be re-consented before re-screening occurs. See [Appendix 1](#) and [Appendix 3](#) for the schedule of screening and pretreatment assessments.

4.5.17.2 Assessments during Treatment

All assessments must be performed on the day of the specified visit, unless a time window is specified in the schedule of assessments (see [Appendix 1](#), [Appendix 2](#), and [Appendix 3](#)). Assessments scheduled on the day of study treatment administration should be performed prior to administration of study treatment, unless otherwise noted in the schedule of assessments. The ATAQ-IPF, SGRQ, and EQ-5D should be self-administered at the investigational site prior to all other non-PRO assessments and before the patient receives any disease-status information or study drug during that assessment. The Borg CR10 Scale should be administered immediately before and after the 6MWT prior to all other non-PRO assessments and before the patient receives any disease-status information or study treatment during that assessment. However, spirometry and DL_{CO} may be performed during Visit 1 before 6MWT at the discretion of the investigator. In all cases, each study assessment should be done in the same order at subsequent visits. See [Appendix 1](#), [Appendix 2](#), and [Appendix 3](#) for the schedules of assessments performed during the minimum and maximum treatment periods.

4.5.17.3 Assessments at Study Completion/Early Termination Visit

The study completion visit occurs as part of the last Safety Follow-up Visit (see [Appendix 1](#), [Appendix 2](#), and [Appendix 3](#)). All patients will be monitored for safety for 18 weeks after receipt of the final dose of lebrikizumab or placebo study treatment.

Patients who choose to prematurely discontinue study drug will be encouraged to remain in the study and complete all remaining assessments. If this is not feasible, the patient should enter and complete the safety follow-up period unless consent has been withdrawn.

Patients who withdraw from the study (regardless of the reason) and refuse safety follow-up will be asked to return to the clinic within 30 days (± 7 days) after the last dose of study treatment for an early termination visit. Refer to [Appendix 1](#), [Appendix 2](#), and

[Appendix 3](#) for the schedules of assessments performed at the study completion or early termination visit.

4.5.17.4 Follow-Up Assessments

After the study completion/early termination visit, adverse events should be followed as outlined in Section 5.5 and Section 5.6. Refer to [Appendix 4](#) for the schedule of assessments performed at the follow-up visit.

4.5.17.5 Assessments at Unscheduled Visits

See [Appendix 1](#), [Appendix 2](#), [Appendix 3](#), and [Appendix 4](#) for assessments that are required in case of an unplanned visit. An unscheduled visit may occur at any time during the study.

4.6 PATIENT, STUDY, AND SITE DISCONTINUATION

4.6.1 Patient Discontinuation

The investigator has the right to discontinue a patient from study drug or withdraw a patient from the study at any time. In addition, patients have the right to voluntarily discontinue study drug or withdraw from the study at any time for any reason. Reasons for discontinuation of study drug or withdrawal from the study may include but are not limited to the following:

- Patient withdrawal of consent at any time
- Any medical condition that the investigator or Sponsor determines may jeopardize the patient's safety if he or she continues in the study
- Investigator or Sponsor determines it is in the best interest of the patient
- Patient noncompliance, such as missing scheduled visits, non-adherence with medications, etc.

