4.6.1.1 Discontinuation from Study Drug

Patients must discontinue study drug if they experience any of the following:

- Pregnancy
- Anaphylactic, anaphylactoid, or other serious hypersensitivity reaction
- Malignancy (including basal or squamous cell carcinoma of the skin or carcinoma in situ)

Patients who discontinue study treatment should continue to complete all scheduled study assessments and if unable or unwilling to complete these assessments should at minimum enter the safety follow-up period. All patients should be followed for safety for 18 weeks after the last dose of lebrikizumab or placebo study treatment. The primary reason for premature study treatment discontinuation should be documented on the appropriate eCRF. Patients who discontinue study treatment prematurely will not be replaced.

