4.6.1.2 Withdrawal from Study

Every effort should be made to obtain information on patients who withdraw from the study. The primary reason for withdrawal from the study should be documented on the appropriate eCRF. Patients will not be followed for any reason after consent has been withdrawn. Patients who withdraw from the study will not be replaced.

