4.1 ANALYSIS POPULATIONS

4.1.1 Intent-to-Treat Population

The intent-to-treat (ITT) population will be comprised of all patients who were randomized in the study. All efficacy analyses will be performed on this population with patients grouped according to the treatment assignment at randomization.

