4.4 EFFICACY ANALYSIS

All efficacy analyses will be performed on the Randomized Population. Unless otherwise specified, data collected during the 52-week placebo-controlled period will be used, regardless of whether the patient remained on treatment or discontinued the study drug early (but remained in the study). Analyses will be performed for Cohort A and Cohort B separately. For hypothesis testing, each cohort will be considered as a separate study and no type I error control will be done across the two cohorts.

For change-from-baseline endpoints, the baseline value will be defined as the measurement at randomization (Visit 2). If the randomization value is not available, the screening (Visit 1) value can be used in its place (last measurement prior to Day 1). For each subject, relative and absolute changes from baseline will be defined as follows:

- Absolute change from baseline = (post-baseline value – baseline value)
- Relative (%) change from baseline = $100 * (\text{post-baseline value} - \text{baseline value}) / (\text{baseline value})$

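### Protocol 4.6.1 lets an investigator end study follow-up for noncompliance or missed visits in a patient who still consents, so scheduled FVC up to Week 52 may be lost unnecessarily

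*Combined protocol and SAP*

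**What the plan says.** Protocol 4.6.1 gives the power broadly: "The investigator has the right to discontinue a patient from study drug or withdraw a patient from the study at any time". It then introduces one list for both acts: "Reasons for discontinuation of study drug or withdrawal from the study may include but are not limited to the following". The last entry is "Patient noncompliance, such as missing scheduled visits, non-adherence with medications, etc". Nothing limits that entry to stopping study drug.

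The rules that follow depend on which act has taken place:

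- **Study drug stopped.** Protocol 4.6.1.1: "Patients who discontinue study treatment should continue to complete all scheduled study assessments". Protocol 3.1.1 and 4.5.17.3 also encourage these patients to stay.
- **Withdrawn from the study.** Protocol 4.6.1.2: "Every effort should be made to obtain information on patients who withdraw from the study". Follow-up is ruled out altogether only once consent has been withdrawn. Under Protocol 4.5.17.3, patients who withdraw for whatever reason and refuse safety follow-up are "asked to return to the clinic within 30 days (± 7 days) after the last dose of study treatment for an early termination visit". No FVC schedule to Week 52 is set for withdrawn patients, and they are not replaced.

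On the analysis side, SAP 4.1.1 states: "The intent-to-treat (ITT) population will be comprised of all patients who were randomized in the study". SAP 4.4 uses data from the placebo-controlled period "regardless of whether the patient remained on treatment or discontinued the study drug early", and a parenthesis directly after these words restricts this to patients who stayed in the study. SAP 4.4.2 handles the remaining gaps under missing at random, from each patient's own slope before visits stopped.

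**The concern.** The plan otherwise tries to keep patients under observation after they stop study drug, and the SAP intends to use what is collected. The shared list allows a different outcome. A patient who misses doses or visits, but has not refused to be followed, can be taken out of the study by the investigator. The retention rule in 4.6.1.1 then no longer applies, and neither does the SAP's provision for off-treatment data.

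The primary estimate for such a patient comes from extrapolating the slope seen before withdrawal. If the unseen decline differs from that slope, and withdrawals differ between arms, the treatment difference is biased. Vital status is exposed as well: time to death is the first key secondary endpoint in SAP 4.4.1, and SAP 4.4.3 censors it no later than the last date the patient was known to be alive. The loss is in part avoidable, because these patients have not declined follow-up.

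**Working it through.** **1. The plan's own power figure.** Inputs from SAP 2.3: SD 8, two-sided 0.05, 1:1 allocation. Standard error of the difference = 8 × √(2/n).

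- Cohort A: n = 75 per arm, SE = 1.31, 3.7/1.31 = 2.83, power = Φ(2.83 − 1.96) = 80.8%.
- Cohort B: n = 165 per arm, SE = 0.88, 2.5/0.88 = 2.84, power = Φ(2.84 − 1.96) = 81.0%.

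Both reproduce the stated 80% or so. The sample size is not in error.

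**2. What is lost for one patient.** Spirometry falls at Weeks 1, 4, 12, 24, 36, 44 and 52 (Protocol Appendices 1 and 3). Safety follow-up spirometry falls 4, 12 and 18 weeks after the last dose (Appendix 4). Take a patient last dosed at Week 20 and then withdrawn for noncompliance:

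- Kept: FVC at baseline and Weeks 1, 4 and 12.
- Possible, if safety follow-up is accepted: 20 + 4 = Week 24, 20 + 12 = Week 32, 20 + 18 = Week 38.
- Possible, if it is refused: one early-termination spirometry at about Week 24.
- Not required in either case: Weeks 44 and 52.

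The SAP takes in assessments up to Week 52 and the model uses continuous time, so off-schedule values can contribute if obtained. The likely loss is the later part of the year.

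**3. Possible bias.** The documents give no withdrawal rate and no slope after withdrawal, so all inputs here are assumed. Let w be the excess share withdrawn in one arm, d the departure of the true slope from the model's extrapolation (points/year), and f the fraction of the year over which the departure acts. Roughly, bias = w × d × f.

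- w = 0.05, d = 3, f = 1: 0.15 points/year; 0.15/2.5 = 6% of the Cohort B target.
- w = 0.05, d = 5, f = 1: 0.25 points/year; 0.25/2.5 = 10%.
- The same with f = 0.5 (withdrawal at mid-year): about 0.075 and 0.125, or 3% and 5%.
- Against the Cohort B planning SE: 0.15/0.88 = 0.17 and 0.25/0.88 = 0.28 standard errors.

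Wider assumptions at f = 1: 0.05 × 2 = 0.1 (4% of the Cohort B target); 0.10 × 4 = 0.4 (16%); 0.15 × 8 = 1.2 (48%). The last needs heavy, one-sided withdrawal and a very large departure.

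**4. Possible loss of power.** As a worst case, let withdrawn patients contribute nothing. At 5%, 10%, 15% and 20% withdrawal, power is 78.8%, 76.6%, 74.3% and 71.7% in Cohort A, and 79.0%, 76.8%, 74.4% and 71.9% in Cohort B. The true loss is smaller, because FVC before withdrawal stays in the model.

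**The case against.** The strongest case against is that the clause permits withdrawal but does not direct it, and that the same entry also serves for stopping drug. Wherever the protocol gives directions for patients off drug, it favours keeping them. For patients who do leave, it asks for effort to obtain information and provides for a further visit with spirometry. All of this stands. Loss is possible, not certain, and it is partial.

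A reader might infer that the clause removes all post-treatment FVC, or that protocol and SAP contradict each other. The documents support neither. Earlier FVC stays in, later spirometry may be obtained, and the SAP openly limits off-treatment data to patients still in the study. The clause works against the aim of retention without conflicting with the wording of the SAP.

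A reader might also infer that data lost this way cannot be missing at random. That does not follow. Worsening already visible in a patient's earlier FVC is compatible with the assumption; only unobserved worsening breaks it, and no passage shows how noncompliance relates to decline. SAP 4.4.5 also plans a placebo-based multiple imputation and a rank analysis that carries the last value forward. These probe the assumption but do not recover the measurements.

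Finally, patients who miss visits may go on missing them whatever the protocol says. That is fair, and it limits the benefit, but it is no reason to let follow-up be ended for them.

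**Conclusion.** The point holds in a limited form. Protocol 4.6.1 allows an investigator to end follow-up for noncompliance or missed visits in a consenting patient. Scheduled FVC from then to Week 52 may be lost, and more of the primary result then rests on missing at random.

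The size cannot be established from the documents. The figure of 0.15 to 0.25 points/year is an illustration that depends on three assumptions: a 5% excess in one arm, a departure of 3 to 5 points/year, and that departure acting for the full year. On the first two, it is an upper value. In Cohort B it is under a third of a standard error. This is a cheap improvement to the conduct rules, not a defect in the sample size or the primary model.

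It would go too far to conclude that follow-up should end only for withdrawn consent, loss to follow-up or death. That would also delete the reasons in 4.6.1 concerning patient safety and best interest, and nothing in this argument supports doing so.

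**What to change.** Split the list in Protocol 4.6.1 into reasons for stopping study drug and reasons for withdrawal from the study. Keep noncompliance and missed visits in the first list only, and state that they are not by themselves grounds for an investigator to withdraw a patient from the study. For these patients, continue FVC and vital-status collection to Week 52 unless consent is withdrawn. Leave the safety and best-interest reasons, and the rules for stopping study drug, as they are.

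The cost is protocol wording, a letter to sites and a few more visits. The reach is narrow: Cohort A was unblinded in May 2016 (Protocol 1.4) and all 507 patients had been enrolled (Protocol 9.3), so only Cohort B patients still in placebo-controlled follow-up can benefit. For withdrawals that have already happened, the primary reason is on the eCRF (Protocol 4.6.1.2) and SAP 4.2 already summarises discontinuation reasons. Reporting investigator withdrawals for noncompliance by arm would show whether the issue arose at all.

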4.6.1.1 Discontinuation from Study Drug

Patients must discontinue study drug if they experience any of the following:

- Pregnancy
- Anaphylactic, anaphylactoid, or other serious hypersensitivity reaction
- Malignancy (including basal or squamous cell carcinoma of the skin or carcinoma in situ)

Patients who discontinue study treatment should continue to complete all scheduled study assessments and if unable or unwilling to complete these assessments should at minimum enter the safety follow-up period. All patients should be followed for safety for 18 weeks after the last dose of lebrikizumab or placebo study treatment. The primary reason for premature study treatment discontinuation should be documented on the appropriate eCRF. Patients who discontinue study treatment prematurely will not be replaced.

4.6.1.2 Withdrawal from Study

Every effort should be made to obtain information on patients who withdraw from the study. The primary reason for withdrawal from the study should be documented on the appropriate eCRF. Patients will not be followed for any reason after consent has been withdrawn. Patients who withdraw from the study will not be replaced.

4.6.2 Study and Site Discontinuation

The Sponsor has the right to terminate this study at any time. Reasons for terminating the study may include but are not limited to the following:

- The incidence or severity of adverse events in this or other studies indicates a potential health hazard to patients
- Patient enrollment is unsatisfactory
- Data recording is inaccurate or incomplete

The Sponsor will notify the investigator if the study is placed on hold or if the Sponsor decides to discontinue the study or development program.

The Sponsor has the right to replace a site at any time. Reasons for replacing a site may include but are not limited to the following:

- Excessively slow recruitment
- Poor protocol adherence
- Inaccurate or incomplete data recording
- Non-compliance with the International Conference on Harmonisation (ICH) guidelines for Good Clinical Practice

